# **Study Protocol Cover Page**

**Official Title: Neurobehavioral Plasticity to Regular Sugar-Sweetened Beverage Intake: An fMRI Experiment**

**NCT Number: NCT03490734**

**Document Date: January 25, 2023**

## **Study Protocol**

### **A. Study Rationale**

Half of Americans consume sugar-sweetened beverages (SSBs) on any given day. Regular SSB intake is considered a contributing factor to excess energy intake, weight gain and obesity, which impacts 70% of Americans. Preclinical and human studies indicate sugar is highly rewarding, as it elicits release of dopamine and opioids in the striatum^6. Multiple brain-based models of food reward-driven obesity have been proposed, largely focusing on striatal response and dopaminergic functioning. While these models have elucidated neural correlates of obesity, data supporting these models rely heavily on observational and cross-sectional studies in small samples. Without rigorous, experimental evidence, there are fundamental gaps in our knowledge about the critical initial period of habit formation as an individual begins to regularly consume a high sugar food. Further, current research frequently utilizes singular methodologies, limiting the understanding of the interrelationships among neural responses, implicit behavior, and the perception of foods. To address these gaps, our team and others have shown that brain response during food intake and food cue exposure are, in part, a function of eating behavior patterns independent of weight status. These observational results dovetail with previous reports examining the impact of weight status providing convergent validity. To better examine the temporal precedence of these effects, we completed a small-randomized controlled trial that assigned daily consumption of SSBs over 3 weeks. Critically, results supported the hypothesis that regular SSB intake causes specific neurobehavioral adaptions that may represent habit formation, which, in theory, would serve to perpetuate consumption. We posit that an improved understanding of the strength, specificity, and persistence of neurobehavioral adaptions that occur in the critical, initial period of SSB consumption are imperative to elucidate the impact of sugar on regulation of intake.

To confirm and extend our preliminary evidence, we propose a rigorous approach that bridges neural, behavioral, and perceptual assessments to evaluate the impact of regular SSB intake. In the proposed randomized controlled trial, 230 young adults (18-28 years old, BMI 18-34) will be assigned to consume branded versions of either an SSB or unsweetened, similarly flavored control beverage daily for 3 weeks. Through this multimodal approach, the proposed experiment will be the first to provide relevant data on strength and specificity of neurobehavioral adaptions associated with regular SSB intake, and the individual factors that predict the degree of these adaptions. The central goals of this proposal are: 1) to determine whether daily intake of SSB results in differential neurobehavioral adaptions compared to baseline response and unsweetened, flavored control beverages, and examine the flavor specificity of these effects; 2) to test whether individual factors previously implicated in obesity moderate neurobehavioral adaptions

### **B. Study Objectives**

**Aim 1:** Test the neurobehavioral adaptions in response to repeated intake of branded SSBs relative to unsweetened, flavored control beverages (USB).

*We hypothesize that daily SSB intake will lead to:*

- a. *increases in parietal/occipital brain response during exposure to the SSB brand;*
- b. *decreased dorsal prefrontal and hippocampal response to the SSB brand;*
- c. *reduced striatal response during receipt of the assigned SSB,*

*relative to baseline and to those who are assigned to consumed the control beverage.*

**Aim 2:** Test whether BMI mediates the neurobehavioral response patterns to the consumed beverages as a function of daily SSB intake relative to baseline and to those who are assigned to consume USB.

*We hypothesize that there will be no significant interaction, such that those individuals with elevated BMI will show no difference than those at a lower BMI in the brain adaptions described in Aim 1.*

**Aim 3:** Test the impact of repeated consumption of SSBs on behavioral responses (reaction time and response inhibition) to the beverage brands measured by the stop sign task (SST).

*We hypothesize that mean reaction time to Go trials will result in a significant interaction of group assignment (sugar vs. control) by pre-/post- daily consumption. Specifically, we hypothesize that the sugar group will show a decreased reaction time to Go trials, representing faster responses relative to the control group and baseline.*

**Aim 4:** Test the impact of repeated consumption of sugar-sweetened beverage on perceptual hedonic and taste ratings.

*We hypothesize that daily beverage intake will lead to:*

- a. *no change in pleasantness and desire ratings as a function of repeated consumption of the assigned beverages.*
- b. *an assignment (sugar vs. control) by time (pre-/post- daily consumption) interaction for desire ratings of the non-assigned beverages. Specifically, we hypothesize that there will be a decrease in desire ratings of the control beverage after having consumed a SSB daily. We expect no change in pleasantness.*

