Explicit hedonic, taste and internal state ratings assessed via visual analog scales (VAS). Explicit hedonic scales were used to evaluate characteristics of the beverages, including pleasantness, desire, sweetness, bitterness, intensity, and familiarity insight into alterations the perceptual hedonic value of the beverages. Measures of internal state: hunger, fullness, thirst, and nausea were also collected. For perceptual hedonic assessments, labeled hedonic scales and generalized labeled magnitude scales provide a ratio-like data with the ability to compare individual differences in a more sensitive way than traditional scales. The participant consumed a small amount of the beverage and completed the associated scale (e.g., pleasantness). Additionally, similar internal state scales were assessed via 200mm cross-modal visual analog scales at all assessments. Scales of all beverages (SSB, USB; both flavors) were collected on the pre- and post-intervention behavioral visits. Scales for assigned beverages only were also collected on the pre- and post-intervention scan visits.

Stop signal task (SST). The Stop-Signal Task measures motor response time, accuracy, and response inhibition. The task was performed on an iPad app where participants underwent 6 total runs at the pre-intervention behavioral visit and at the post-intervention behavioral visit. Three of these runs were of their assigned condition, where the logo of their assigned beverage

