## **Statistical Analysis Cover Page**

**Official Title: Neurobehavioral Plasticity to Regular Sugar-Sweetened Beverage Intake: An fMRI Experiment**

**NCT Number: NCT03490734**

**Document Date: January 25, 2023**

## **Statistical Analysis Plan**

### **A. Sample Size and Power**

Data collection was ended early due to COVID-19 (ending March 2020), resulting in a lower than anticipated sample size (160 vs. 230), which may impact results, specifically, measures of individual differences. As our sample was smaller than anticipated we performed a sensitivity analysis using Gpower (ver. 3.1.9.7, Heinrich Heine University Düsseldorf) for the primary hypothesis using alpha = 0.05, power of 0.80 and a total sample of 123 (accounting for missing data, incomplete data collection, etc.), and we are still able to detect effect of 0.25. Inclusion Criteria: Potential participants were eligible for the study if they had BMI scores between 18 and 34 at baseline. Exclusion Criteria: Individuals with probable current Axis I psychopathology or any fMRI contra-indicators (e.g., metal implants, braces) were excluded. Those with a probable Axis I diagnosis will be provided with treatment referral information and encouraged to seek treatment, current regular use (3 or more times a week) of psychoactive drugs (e.g., cocaine, marijuana, nicotine), regular smoking, serious medical problems (e.g., cancer, diabetes), dietary practices that do not allow for intake of intervention beverages.

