### **B. Analysis Plan**

#### *1. Primary and Secondary Outcomes*

Behavioral data analysis (stop-signal reaction time & perceptual ratings of beverages): Continuous variables from the stop signal task and the visual analogue scale (VAS) ratings were summarized by descriptive statistics (e.g., mean, SD, range, median), examined via graphical analyses (e.g. histogram, Q-Q plot) and analyzed to assess the normality of the data. Data transformation of continuous variables were used as necessary. Model assumptions and potential outliers were analyzed with various modeling diagnostics and plotting techniques. Two analytic datasets are used. Participants that provided data at baseline and follow-up are used in a completers analysis (CA). An intent-to-treat (ITT) dataset, including all participants that were consented and completed one assessment, are also used. In that analysis, missing data are addressed via multiple imputation methods. Of note, in both the CA and ITT all subjects are included independent of their adherence to the intervention.

For **Aim 3**, reaction times from the stop signal task (SST) are analyzed. Following previous standards, reaction times <50 milliseconds are excluded (occurred prior to imputation). As we are not analyzing inhibition (inhibition accuracy/SSRT), no other exclusion criteria were used. Data from pre- and post-intervention SST measures are analyzed using PROC MIXED implemented in SAS (Version 9.4, Cary, NC). All available data from those completing the pre- and post-intervention behavioral visits (separate from the scan assessments) are used in the completers analysis. All those who consented are included in the ITT analysis with missing data imputed. Outcome variables assessed via the SST task are: mean reaction time, standard deviation, go accuracy of the assigned beverage (pre-/post-intervention). Each of the outcome variables is entered into 2x2 repeated measure mixed models, including group-by-time interactions. Control variables of no interest to be included are BMI, assigned flavor, and gender. Interactions are probed for pairwise comparisons using least-squared mean comparisons, specifically of a priori contrasts of interest: between-group baseline differences and follow-up differences, and within-assignment change from pre- to post-intervention. Bonferroni-adjusted two-tailed *p*-values less than 0.05 are considered significant.

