For **Aim 4**, perceptual hedonic, taste and internal state ratings (assessed using visual analog scales (VAS)) are analyzed. Data from pre- and post-intervention perceptual ratings are

analyzed using PROC MIXED implemented in SAS (Version 9.4, Cary, NC). Pleasantness and Desire of the assigned beverage (pre-/post-intervention) are each entered into 2x2 repeated measure mixed models, including group-by-time interactions. Control variables of no interest to be included are BMI, assigned flavor, gender, and thirst. Four pairwise comparisons of interest (pre- and post-intervention differences by intervention assignment and within-assignment change over time) are probed. Tukey-adjusted two-tailed  $p$ -values less than 0.05 are considered significant.

**fMRI data preprocessing:** Neuroimaging data were preprocessed using the fMRIPrep pipeline. DICOMS were converted to the Brain Imaging Data Structure (BIDS file structure), then preprocessed using fMRIPrep. Prior to preprocessing, the first four volumes of each functional run were trimmed. fMRIPrep preprocessing included skull stripping using Advanced Normalization Tools (ANTs); tissue segmentation using FSL's Automated Segmentation Tool (FAST); and spatial normalization to Montreal Neurological Institute (MNI) 152-Asymmetrical space using ANTs' registration option. Functional data were co-registered to anatomical data using FSL's FMRIB's Linear Image Registration Tool (FLIRT) with boundary-based registration. Functional data were additionally motion corrected using FSL's MCFLIRT and corrected for fieldmap distortion. In FSL, final preprocessing included spatial smoothing using a 5mm full width half maximum isotropic Gaussian kernel, high-pass filtering, adding temporal derivatives, adjusting for autocorrelation, and adjusting for nuisance regressors, including the 6 motion parameters, 6 anatomical component-based noise correction regressors (aCompCor), and high motion time points (FD>0.5mm). A functional run for a subject was excluded if >30% of total volumes were flagged as high motion points.

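### Aim 2 and hypothesis 4a predict no effect, but the SAP plans only difference tests with no interval or rule for reading a null result, and it names no model for hypothesis 4b

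*Protocol*

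**What the plan says.** Three predictions in Protocol section B are of no effect.

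- Aim 2: "We hypothesize that there will be no significant interaction, such that those individuals with elevated BMI will show no difference" from those with lower BMI in the Aim 1 brain adaptions.
- Hypothesis 4a: "no change in pleasantness and desire ratings as a function of repeated consumption of the assigned beverages".
- Hypothesis 4b concerns the non-assigned beverages. It predicts a group-by-time interaction for desire and then adds: "We expect no change in pleasantness".

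The SAP, section B.1, plans the following.

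- Aim 2: the assignment-by-BMI interaction at level 3, adjusted for flavor, gender, thirst and pleasantness, judged by whole-brain TFCE at a family-wise error rate of 0.05. Parameter estimates are plotted for significant response only.
- Aim 4: "Pleasantness and Desire of the assigned beverage (pre-/post-intervention) are each entered into 2x2 repeated measure mixed models", followed by four Tukey-adjusted pairwise comparisons at two-tailed 0.05.
- Ratings in general: descriptive summaries that include means and SDs.

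No model is named for a non-assigned beverage, yet Protocol section G states: "Scales of all beverages (SSB, USB; both flavors) were collected on the pre- and post-intervention behavioral visits". Neither document mentions a confidence interval, an equivalence rule or any other rule for a null result. SAP section A reports 160 participants against 230 planned, "which may impact results, specifically, measures of individual differences". Its sensitivity analysis uses 123 participants and covers the primary hypothesis only.

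**The concern.** When the predicted outcome is a null, a test for a difference gives little support by being non-significant. No effect and a small effect that went undetected produce the same result, and a smaller sample makes that result more likely. The loss of sample here therefore works in favor of these hypotheses.

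The problem is sharpest for Aim 2. If the prediction comes true, no cluster is significant, nothing is plotted, and the reader gets no regional estimate and no measure of its precision. A sentence saying that BMI does not moderate the adaptions would rest on p>0.05 alone. This matters because moderation by individual factors is one of the two central goals set out at the end of Protocol section A.

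Hypothesis 4b has a different gap. Its data exist, but no analysis is specified for either its desire prediction or its pleasantness prediction.

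**Working it through.** **1. The plan's own figure.** Inputs from SAP section A: alpha 0.05, power 0.80, N=123, detectable effect 0.25, metric not named.

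- Two-group comparison, noncentral F with 1 and 121 df and λ = N·f²: 80% power needs f = 0.2546. Power at f = 0.25 is 0.785.
- Correlation by Fisher z: r = tanh[(1.960 + 0.842)/√120] = 0.2503.

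Both round to 0.25, so the figure reproduces. It refers to detecting the primary effect. It does not say how precisely a BMI interaction or a rating change would be estimated.

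**2. Aim 2, illustration.** Assumptions: one region, one uncorrected two-sided 5% test, and partial correlations of 0.15 and 0.20 for group-by-BMI. The documents give no effect size. The model has 8 parameters (intercept, group, BMI, group-by-BMI, flavor, gender, thirst, pleasantness). The miss probability comes from the noncentral F with 1 and N−8 df and λ = N·r²/(1−r²). At N=123, λ = 123 × 0.0225/0.9775 = 2.83 for r = 0.15, and 123 × 0.04/0.96 = 5.13 for r = 0.20.

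| N | Miss, r=0.15 | Miss, r=0.20 | 95% half-width at r=0 |
|---|---|---|---|
| 123 | 61% | 39% | 0.18 |
| 160 | 52% | 27% | 0.16 |
| 230 (planned) | 37% | 13% | 0.13 |

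The half-width is tanh[1.96/√(N−6−3)], with 6 partialled terms. At N=123 it is tanh(1.96/√114) = 0.18.

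**3. Hypothesis 4a, illustration.** Assumptions: a shift of 0.3 SD of change (no SD is given) and 61 or 80 per arm (about half of 123, and half of 160). The Tukey critical value for 4 means is 2.605 (120 df) or 2.597 (158 df). Misses come from the noncentral t.

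| Test | Noncentrality | Miss, 61 per arm | Miss, 80 per arm |
|---|---|---|---|
| Overall time effect, both arms shift | 0.3√(2n) | 9% | 4% |
| Tukey comparison in the one arm that shifts | 0.3√n | 60% | 46% |
| Group-by-time, one arm shifts | 0.3√(n/2) | 62% | 53% |

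A common shift would usually be found by the overall time effect, although the SAP does not list that effect among its comparisons. A shift in one arm would often be missed. The 95% half-width for change within an arm is 1.96/√61 = 0.25 SD or 1.96/√80 = 0.22 SD.

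**4. Hypothesis 4b.** No arithmetic applies. Protocol section G collects the ratings of all beverages before and after. The Aim 4 text in SAP section B.1 names outcomes for the assigned beverage only.

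**The case against.** The strongest reply is that the documents never say a non-significant result will be reported as proof of no effect. The first half of the Aim 2 sentence predicts only the absence of a significant interaction, which the planned test answers literally, and the SAP itself warns about individual differences in the smaller sample. All of this is correct. A reader might infer that the sponsor intends to read p>0.05 as no effect; the documents do not support that, because they are silent. What remains is that the same sentence goes on to predict no difference by BMI, and the planned outputs cannot support that part.

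For the ratings, means and SDs are planned and the mixed models yield standard errors, so intervals follow directly. That stands: for 4a the gap is mainly one of reporting.

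The Aim 2 miss rates might be taken as those of the planned analysis. They are not. Whole-brain TFCE could detect more or less than one uncorrected regional test, and N=123 is stated for the primary hypothesis only.

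It might also be inferred that 4b, like 4a, gets a difference test without an equivalence rule. The documents do not go that far. The SAP's opening Aim 4 sentences say generally that perceptual ratings go into mixed models, so an analysis may be intended, but none is named for the non-assigned beverages.

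Finally, a formal equivalence rule is tempting. Collection ended in March 2020 and the SAP is dated January 2023, so a margin set now would probably be post hoc. Regional means also cannot exclude focal moderation. That objection stands, and the fix below asks for no such rule.

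**Conclusion.** The concern holds for Aim 2 and 4a in this form: non-significance cannot by itself support the predicted nulls, and the SAP plans neither an interval nor a rule for reading them. The gap is substantial for Aim 2, where a null leaves no planned regional summary, and smaller for 4a. For 4b the gap is a missing model specification. The primary Aim 1 test is unaffected.

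The size is illustrative. An uncorrected single-region test misses partial correlations of 0.15 and 0.20 in 61% and 39% of trials at N=123, or 52% and 27% at N=160. It rests on assumed effect sizes, on N=123 carrying over to Aim 2, and on a test simpler than the one planned. The conclusion itself depends on none of these figures. The change should be made, because it decides what may be concluded from the results that the sponsor expects.

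**What to change.** 1. **Aim 2.** Keep the TFCE maps. Add, whether or not any cluster is significant, the group-by-BMI estimate with its 95% interval for mean pre-to-post change in each region named in Aim 1, with the SAP covariates. Use the logo contrast for parietal/occipital, dorsal prefrontal and hippocampal regions, and the taste contrast for striatum. Fix the atlas regions before estimates are seen, or say that this was not possible.
2. **Aim 4.** Report change in pleasantness and desire of the assigned beverage, by arm and overall, with 95% intervals in the completers and ITT sets. Add the same 2x2 mixed model for desire and pleasantness of the non-assigned beverage, stating which flavor is meant, since both were rated.
3. **Interpretation.** State that a non-significant result on these hypotheses is inconclusive by itself and is read through its interval. Adopt no margin-based rule for claiming absence of moderation. If any equivalence statement is made, limit it to mean regional response and label a margin set after data collection as post hoc.

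The cost is small: region averages from level-2 images already planned, one regression per region, intervals from models already planned, and one added model each for desire and pleasantness. The drawbacks are wide intervals (about r ±0.18 at N=123 or ±0.16 at N=160) and dilution. If half a region carries r=0.30 and the noise of the mean is unchanged, the regional mean shows about 0.15. The report should therefore say that a narrow regional interval does not exclude focal moderation.

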### C. Study Design

We propose to use a randomized control trial design and recruit 230 18-28 year old men and women over a 42-month period to address the proposed aims. Participants will be randomly assigned to an experimental condition (sugar-sweetened beverage [SSB] or unsweetened, flavored control [USB]) and then to one of two flavors within their experimental condition. This results in 4 cells: two flavors high-sugar beverages (n=115; 58/57 for each flavor of SSB) and the same two flavors of unsweetened control beverages (n=115; 58/57 for each flavor of control). The two-tiered randomization process allows for a fully powered test of the effects of SSB consumption (n=115) versus unsweetened control (n=115; Aim 1) and individual difference factors (Aims 2-4). Participants will complete the pre-intervention assessments (see **Table 1 & Study Procedures**), then begin the intervention which will include the daily consumption of their flavored beverage for 21 days. Following the intervention, participants will come back in the lab to complete the post-intervention assessments (see **Study Procedures**).

### D. Study Duration, Enrollment and Number of Subjects

For each participant, the study will include 2 pre-intervention visits, 2 post-intervention visits, and 9 in-lab assessments during the 21-day intervention period. Total study duration will be approximately two years. We will recruit 230, 18-28-year-old healthy individuals. Stratified randomization techniques will be used to distribute: 1) male & females, 2) those with a BMI > 26.1 & those with a BMI < 26.1 equally across the 2 experimental conditions (SSB vs. unsweetened beverage) and then to the two flavors within each experimental condition. BMI of 26.0 was selected as it is the midpoint of inclusion criteria 18 < BMI < 34. Experimental and flavor conditions will be blinded to those performing analyses.

## E. Study Population

To best capture the local population, we will require that participants have BMI between 18-34 kg/m^2. Following our previous studies, we will exclude young adults who report current: a) contraindications of fMRI (e.g., metal implants), b) serious medical problems (e.g., diabetes) assessed using a standard review form, c) any previous treatment for eating disorders or drug or alcohol abuse/addiction, d) current major psychiatric disorders (e.g., depression, generalized anxiety disorder), e) current dieting, f) regular smoking, and g) dietary practices that do not allow intake of intervention beverages. We will provide samples of the beverages during the consent process to ensure all the participants are willing to adhere to protocols.

Table 1. Assessments	Pre-intervention (2 separate visits)	Intervention (21 days)	Post-intervention (2 separate visits)
fMRI scan	•		•
Fasting blood draw	•		•
Ad lib sugary food intake	•		•
Daily beverage intake		•	
Height/Weight	•		•
Behavioral tasks (incl. SST)	•		•
Explicit perceptual & hedonic ratings	•	X	•
Intake & activity patterns	•		•

X = assigned beverage only

